17.6 Other Safety Data

17.6.1 Vital Signs

Vital signs results will be listed with a flag marking the clinically notable values for each of the following parameters:

Clinically notable elevated values

- Systolic BP: >=180 mmHg and an increase >=20 mmHg from baseline
- Diastolic BP: >=105 mmHg and an increase >=15 mmHg from baseline.
- Weight: Increase from baseline of 10%
- Heart rate: >=120 bpm with increase from baseline of >=15 bpm
- Temperature: >38 °C

Clinically notable below normal values

- Systolic BP: <=90 mmHg and a decrease >=20 mmHg from baseline
- Diastolic BP: <=50 mmHg and a decrease >=15 mmHg from baseline
- Weight: decrease from baseline of >=10%
- Heart rate: <=50 bpm with decrease from baseline of >=15 bpm
- Temperature: <35 °C

The number of subjects with at least one clinically notable value as defined above will be summarized in a table.

F

TPL N°: eTPL SA-02-01 TPL Version: 02 Of SOP SA-02.08

OF SOP SA-02.08

TPL Effective Date: 31 Mar 2016

Approved in Vault: 6/30/2021

17.6.2 Physical Findings

Baseline physical examination will be tabulated. All physical examination results will be listed.

Version: 4.0

Page 35 of 46

Descriptive statistics (actual values and changes from baseline) over time will be given for body weight as it is important for the dosing.

17.6.3 ECG

ECG interpretation (Normal / Abnormal, not clinically significant, / Abnormal, clinically significant) and ECG measurements (RR, QT, QTcF, QTcB, PR and QRS) will be tabulated/summarized by visit and ECG time point (Before infusion, At the end of infusion, 2 hours after end of infusion, 5 hours after end of infusion). The three 12-lead ECG performed at each visit/time point will be combined as one measurement using the average of the three results (for ECG measurements), and the worst outcome of the three results for ECG interpretation.

Categorical analysis of QT, QTcB and QTcF interval data based on the number of subjects meeting or exceeding predefined limits in terms of absolute QT, QTcB and QTcF intervals (>450 ms or >480 ms or >500 ms) or changes from baseline (change of >30 ms or >60 ms) will be presented at baseline and at any post-baseline visit.

Additionally, categorical analysis of PR interval data based on the number of subjects meeting or exceeding predefined limits in terms of absolute PR (>200 ms or >220 ms) or changes from baseline (change of >25%) will also be presented at baseline and at any post-baseline visit.

Lastly, categorical analysis of QRS interval data based on the number of subjects meeting or exceeding predefined limits in terms of absolute QRS (>110 ms or >120 ms) or changes from baseline (change of >25%) will also be presented at baseline and at any postbaseline visit.

A listing of these subjects will be produced.

QTcB and QTcF will also be presented graphically using a mean-se plot over time for change from baseline values.

ECOG Performance Score 17.7

ECOG performance score assessments will be listed and summarized descriptively over time.

17.8 Hepatitis B, C and Cytomegalovirus Serology

All hepatitis B, C, and CMV serology data will be listed.

17.9 **Pregnancy Test**

TPL Effective Date: 31 Mar 2016

Pregnancy test results will be tabulated presenting the number and percentage of subjects with at least one positive or borderline versus all negative. The positive or borderline results will be included per visit.

All pregnancy test data will be listed.

TPL N°: eTPL SA-02-01 TPL Version: 02 Of SOP SA-02.08

	Genmab - GCT1021-01	Version: 4.0
18.	Evaloratory Analysis	
10.	Exploratory Analyses	

TPL N°: eTPL SA-02-01 Of SOP SA-02.08 TPL Effective Date: 31 Mar 2016 TPL Version: 02

Approved in Vault: 6/30/2021

Table 6.

TPL N°: eTPL SA-02-01 Of SOP SA-02.08 TPL Effective Date: 31 Mar 2016 TPL Version: 02

19. References

- 1. http://www.consort-statement.org/
- 4. Scher HI, Morris MJ, Stadler WM, et al. Trial Design and Objectives for Castration-Resistant Prostate Cancer: Updated Recommendations From the Prostate Cancer Clinical Trials Working Group 3. J Clin Oncol. Apr 202016; 34(12): 1402-1418.

TPL N°: eTPL SA-02-01 TPL Version: 02 Of SOP SA-02.08

TPL Effective Date: 31 Mar 2016 Approved in Vault: 6/30/2021

Version: 4.0

20. List of Tables/Graphs/Listings

20.1 List of Statistical Tables

General	Dose- Escalation Part	Expansion Part
Table 14.01.01: Screen Failures	X	X
Table 14.01.02: Analysis Sets	X	Х
Table 14.01.03.01: Subject Treatment Disposition	X	Χ
Table 14.01.03.02: Subject Study Disposition	X	Х
Table 14.01.04: Important Major Protocol Deviations	Х	Х
Table 14.01.04.01: Covid-19 Protocol Deviations (if needed)	Х	Х
Table 14.01.05: Demographic Characteristics	Х	Х
Table 14.01.06: Baseline Disease Characteristics	X	X
Table 14.01.07: Biopsy Information	X	X
Table 14.01.08.01: Medical History (Ongoing) – by SOC and Preferred Term	X	X
Table 14.01.08.02: Medical History (Past) – by SOC and Preferred Term	X	X
Table 14.01.08.03: Surgical History – by SOC and Preferred Term	X	X
Table 14.01.09.01: Prior Cancer Therapies - Summary	X	X
Table 14.01.09.02: Prior Systemic Cancer Therapies – All – by ATC1 Name and ATC 4 Name	X	X
Table 14.01.09.03: Prior Treatment Lines of Systemic Cancer Therapies - by ATC1 Name and ATC 4 Name	Х	Х
Table 14.01.09.04: Prior Cancer Surgeries – by SOC and Preferred Term	Х	X
Table 14.01.09.05: Prior Radiation Therapies – by SOC and Preferred Term	Х	X
Table 14.01.10.01: Subsequent Systemic Cancer Therapies – by ATC1 Name and ATC 4 Name	Х	Х
Table 14.01.10.02: On-Study Cancer Surgeries – by SOC and Preferred Term	X	Х
Table 14.01.10.03: On-Study Radiation Therapies – by SOC and Preferred Term	X	X
Table 14.01.11: Procedures – by SOC and Preferred Term	Х	X
Table 14.01.12.01: Prior Medications – by ATC1 Name and ATC 4 Name	Х	Х
Table 14.01.12.02: Concomitant Medications – by ATC1 Name and ATC 4 Name	X	X
Table 14.01.12.03: Concomitant Medications for Blood Transfusion – by ATC1 Name	X	X
and ATC 4 Name		^
Table 14.01.13: Baseline Physical Examinations	Х	Х
Efficacy Evaluation	Dose- Escalation Part	Expansion Part
Table 14.02.01.01: Response According to RECIST 1.1 – Investigator - Confirmed Responses	Х	Х
Table 14.02.01.02: Response According to RECIST 1.1 – Investigator – All Responses	X	Χ
Table 14.02.02: CA-125 Response	X	Χ
Table 14.02.03.01: Response According to RECIST 1.1 and CA-125 – Investigator - Confirmed Responses (Expansion Part only)		Х
Table 14.02.03.02: Response According to RECIST 1.1 and CA-125 – Investigator - All Responses (Expansion Part only)		Х
Table 14.02.04.01: Progression Free Survival According to RECIST 1.1 – Investigator	X	X
Table 14.02.04.02.xx: Progression Free Survival According to RECIST 1.1 by Subgroups – Investigator (Expansion Part only)		X
Table 14.02.05: Time to Confirmed Response According to RECIST 1.1 – Investigator (Expansion Part only)		X
Table 14.02.06: Duration of Confirmed Response According to RECIST 1.1– Investigator (Expansion Part only)		X
Table 14.02.07: Time to RECIST 1.1 and CA-125 Combined Response – Investigator - (Expansion Part only)		X
Table 14.02.08.01: Overall Survival	X	Χ
Table 14.02.08.02: Overall Survival by Subgroups (Expansion Part only)		Х
Table 14.02.09: CA-125 – Descriptive Statistics	Х	X
Table 14.02.10.a: H-Score in Membrane – Descriptive Statistics		Х
Table 14.02.10.b: H-Score in Cytoplasm – Descriptive Statistics		X
Table 14.02.11:		
Table 14.02.12.01: Peripheral Immune Phenotyping: neutrophils/lymphocytes – Descriptive Statistics		Х

Page 39 of 46

TPL N°: eTPL SA-02-01 Of SOP SA-02.08 TPL Effective Date: 31 Mar 2016

Approved in Vault: 6/30/2021

TPL Version: 02

Table 14.02.12.02: Peripheral Immune Phenotyping: monocytes/lymphocytes – Descriptive Statistics		X
Pharmacokinetics	Dose- Escalation Part	Expansion Part
Table 14.02.13.01: Plasma/Serum Concentration of Enapotamab Vedotin (Conjugated, mg/L) – Descriptive Statistics	Х	Х
Table 14.02.13.02: Plasma/Serum Concentration of Enapotamab Vedotin (Total, mg/L) – Descriptive Statistics	Х	Х
Table 14.02.13.03: Plasma/Serum Concentration of Free Toxin (MMAE, ng/L) – Descriptive Statistics	Х	Х
Table 14.02.14.01: PK Parameters over Time - Enapotamab Vedotin (Conjugated) - Descriptive Statistics	Х	
Table 14.02.14.02: PK Parameters over Time - Free Toxin (MMAE) - Descriptive Statistics	X	
Safety Evaluation	Dose- Escalation Part	Expansion Part
Table 14.03.01: Primary Endpoint: Summary of DLTs – Dose-Escalation Part	Х	
Table 14.03.02: Enapotamab Vedotin Administration	Х	Х
Table 14.03.03.01: Summary of Adverse Events	X	X
Table 14.03.03.02: Summary of Adverse Events – 1.0 mg/kg and 2.2 mg/kg arms	X	X
Table 14.03.04.01.01: Treatment-Emergent Adverse Events - by PT	X	X
Table 14.03.04.01.02: Most Frequent (20%) Treatment-Emergent Adverse Events - by PT	X	X
Table 14.03.04.02: Treatment-Emergent Adverse Events - by SOC and PT	X	Х
Table 14.03.04.03: Treatment-Emergent Adverse Events - by SOC and PT and highest NCI-CTCAE Grade	Х	Х
Table 14.03.04.04: Adverse Events during Follow-up Period – by SOC and PT and highest NCI-CTCAE Grade	Х	Х
Table 14.03.05.01: Enapotamab Vedotin Related TEAEs - by PT	Х	X
Table 14.03.05.02: Enapotamab Vedotin Related TEAEs – by SOC and PT	Х	X
Table 14.03.05.03: Enapotamab Vedotin Related TEAEs - by SOC and PT and highest NCI-CTCAE Grade	Х	Х
Table 14.03.05.04: Enapotamab Vedotin Related Adverse Events during Follow-up Period – by SOC and PT and highest NCI-CTCAE Grade	Х	Х
Table 14.03.06.01: NCI-CTCAE grade ≥3 TEAEs - by PT	X	X
Table 14.03.06.02: Most Frequent (5%) NCI-CTCAE grade ≥3 TEAEs - by PT	X	Х
Table 14.03.06.03: NCI-CTCAE grade ≥3 TEAEs - by SOC and PT	X	Х
Table 14.03.06.04: Enapotamab Vedotin Related NCI-CTCAE grade ≥3 TEAEs - by PT	X	Х
Table 14.03.07.01: TEAEs Leading to Permanent Discontinuation of Trial Treatment - by PT	Х	Х
Table 14.03.07.02: TEAEs Leading to Drug Interruption of Trial Treatment - by PT	Х	Х
Table 14.03.07.03: TEAEs Leading to Dose Reduction of Trial Treatment - by PT	X	X
Table 14.03.08: TEAEs of Special Interest – Selection Criteria and SMQs	X	X
Table 14.03.08.01: TEAEs of Special Interest – by AESI Type and PT	X	X
Table 14.03.08.02: TEAEs of Special Interest – by AESI Type, PT and highest NCI-CTCAE Grade	X	X
Table 14.03.08.03: Enapotamab Vedotin Related TEAEs of Special Interest – by AESI Type and PT	X	X
Table 14.03.08.04: NCI-CTCAE grade ≥3 TEAEs of Special Interest – by AESI Type and PT	Х	Х
Table 14.03.08.05: Serious TEAEs of Special Interest – by AESI Type and PT	Х	X
Table 14.03.08.06: TEAEs of Special Interest Leading to Permanent Discontinuation of Trial Treatment - by AESI Type and PT	Х	Х
Table 14.03.08.07: TEAEs of Special Interest by Cycle - by AESI Type and PT	X	X
Table 14.03.08.08: Time to Onset of First TEAE of Special Interest – by AESI Type, with Outcome of Resolution and Time to Resolution	X	X
Table 14.03.08.09: Constipation and Prophylactic Laxatives	Х	Х
Table 14.03.08.10: Neutropenia and Prophylactic G-CSF	X	X
Table 14.03.09.01: Serious TEAEs - by PT	X	X
Table 14.03.09.02: Enapotamab Vedotin Related Serious TEAEs - by PT	X	X
Table 14.03.09.03: Serious TEAEs Leading to Permanent Discontinuation of Trial	X	X
Treatment - by PT	1	l ,

Approved in Vault: 6/30/2021

Table 14.03.09.04: Serious Adverse Events – by SOC and PT and highest NCI-CTCAE Grade	Х	Х
Table 14.03.09.05: Enapotamab Vedotin Related Serious Adverse Events – by SOC and PT and highest NCI-CTCAE Grade	Х	X
Table 14.03.09.06: Serious Adverse Events during Follow-up Period – by SOC and PT and highest NCI-CTCAE Grade	Х	Х
Table 14.03.10.01: Fatal TEAEs - by PT	Х	Х
Table 14.03.10.02: Enapotamab Vedotin Related Fatal TEAEs - by PT	Х	X
Table 14.03.11: Deaths	X	X
Table 14.03.12: Subject Diary Data including Prophylactic Laxatives	X	X
Table 14.03.13.xx: Biochemistry Laboratory Results - Shift Table from Baseline NCI-CTCAE Grade to Highest Post-Baseline NCI-CTCAE Grade	X	X
Table 14.03.14.xx: Biochemistry Laboratory Results - Shift table from Baseline to Maximum/Minimum Post-Baseline Abnormality	Х	Х
Table 14.03.15.xx: Hematology Laboratory Results - Shift Table from Baseline NCI-CTCAE Grade to Highest Post-Baseline NCI-CTCAE Grade	Х	Х
Table 14.03.16.xx: Hematology Laboratory Results - Shift table from Baseline to Maximum/Minimum Post-Baseline Abnormality	Х	Х
Table 14.03.17.xx: Coagulation factors Laboratory Results - Shift Table from Baseline NCI-CTCAE Grade to Highest Post-Baseline NCI-CTCAE Grade	Х	X
Table 14.03.18.xx: Coagulation factors Laboratory Results - Shift table from Baseline to Maximum/Minimum Post-Baseline Abnormality	Х	X
Table 14.03.19: NCI-CTCAE Grade 3/4 Laboratory Results	X	X
Table 14.03.20: Subject Incidence of Drug Induced Liver Laboratory Abnormalities	Х	X
Table 14.03.21: Vital Signs Abnormalities	X	X
Table 14.03.22: Body Weight over Time - Descriptive Statistics	Х	X
Table 14.03.23.01: ECG Measurements over Time – Descriptive Statistics	Х	X
Table 14.03.23.02: ECG Abnormalities over Time	Х	X
Table 14.03.24: ECOG Performance Score over Time	Х	X
Table 14.03.25: Pregnancy Test Results over Time	Х	X
Exploratory	Dose- Escalation Part	Expansion Part
Table 14.04.01.01.a:		
Table 14.04.01.01.b:		
Table 14.04.01.02.a:		
Table 14.04.01.02.b:		
Table 14.04.01.03.a:		
Table 14.04.01.03.b:		
Table 14.04.02.01: Table 14.04.02.02:		
Table 14.04.02.03:		

 $^{^{\}ast}$ Only most frequent AEs (> X% of Any Grade overall) will be included. The X% will be defined at the time of the analysis programming.

TPL N°: eTPL SA-02-01 TPL Version: 02

Of SOP SA-02.08
TPL Effective Date: 31 Mar 2016
Approved in Vault: 6/30/2021

20.2 List of Graphs

General	Dose- Escalation Part	Expansion Part
Graph 14.01.01:		
Efficacy Evaluation	Dose- Escalation Part	Expansion Part
Graph 14.02.01.01: Response According to RECIST 1.1 – Subgroup Analysis – Investigator (Expansion Part only)		Х
Graph 14.02.01.02: Clinical Benefit at week 12/16 – Subgroup Analysis – Investigator (Expansion Part only)		Х
Graph 14.02.02.01: PFS According to RECIST 1.1 – Kaplan-Meier Curves– Investigator	X	X
Graph 14.02.02.02.xx: PFS According to RECIST 1.1 – Kaplan-Meier Curves - Subgroup Analysis – Investigator (Expansion Part only)		X
Graph 14.02.03: Time to Confirmed Response according to RECIST 1.1 – Investigator (Expansion Part only)		Х
Graph 14.02.04: DoR According to RECIST 1.1 – Kaplan-Meier Curves – Investigator (Expansion Part only)		Х
Graph 14.02.05: Time to RECIST 1.1 and CA-125 Combined Response – Kaplan- Meier Curves – Investigator (Expansion Part only)		Х
Graph 14.02.06: Events over Time		X
Graph 14.02.07.01: Overall Survival – Kaplan-Meier Curves	Х	X
Graph 14.02.07.02.xx: Overall Survival – Kaplan-Meier Curves - Subgroup Analysis		Х
Graph 14.02.08.01.xx: Tumor Shrinkage: Percent Change in Tumor Size Compared to Baseline – Investigator - Individual Profiles	Х	Х
Graph 14.02.08.02.xx: Tumor Shrinkage: Best Percent Change in Tumor Size Compared to Baseline – Investigator	X	X
Graph 14.02.09.01: CA-125: Actual Values	X	X
Graph 14.02.09.02: CA-125: Percent Change from Baseline	X	X
Graph 14.02.09.03.xx: CA-125: Percent Change from Baseline - Individual Profiles	X	X
Graph 14.02.09.04: Best Percent Change in CA-125 Marked with Best Overall Response - Investigator	Х	Х
Graph 14.02.10.01.a:	_	
Graph 14.02.10.01.b:	_	
Graph 14.02.10.02.a:	_	
Graph 14.02.10.02.b:	_	
Graph 14.02.10.03.a:	_	
Graph 14.02.10.03.b:	_	
Graph 14.02.11.01:	_	
Graph 14.02.11.02:	_	
Graph 14.02.11.03:	_	
Graph 14.02.12:		
Pharmacokinetics	Dose- Escalation Part	Expansion Part
Graph 14.02.13.01: Plasma/Serum Concentration of Enapotamab Vedotin (Conjugated) – PK Profiles – Dose-Escalation Part	X	X
Graph 14.02.13.02: Plasma/Serum Concentration of Enapotamab Vedotin (Total) – PK Profiles- – Dose-Escalation Part	Х	Х
Graph 14.02.13.03: Plasma/Serum Concentration of free toxin (MMAE) – PK Profiles – Dose-Escalation Part	Х	Х
Graph 14.02.14.01: Plasma/Serum Concentration of Enapotamab Vedotin (Conjugated)	Х	Х
Graph 14.02.14.02: Plasma/Serum Concentration of Enapotamab Vedotin (Total)	Х	Х
Graph 14.02.14.03: Plasma/Serum Concentration of free toxin (MMAE)	Х	X
Graph 14.02.15.01.xx: PK Parameters of Enapotamab Vedotin (Conjugated) - <pk parameter=""></pk>	Х	
Graph 14.02.15.02.xx: PK Parameters of Free Toxin (MMAE) - <pk parameter=""></pk>	Х	

TPL N°: eTPL SA-02-01 TPL Version: 02 Of SOP SA-02.08 TPL Effective Date: 31 Mar 2016 Approved in Vault: 6/30/2021

Version: 4.0

Safety Evaluation	Dose- Escalation Part	Expansion Part
Graph 14.03.01: Summary of DLTs – Dose-Escalation Part	X	
Graph 14.03.02: Duration of Exposure - Kaplan-Meier Curves	Х	Х
Graph 14.03.03: Time to First TEAE of Special Interest	X	X
Graph 14.03.04: TEAEs of Special Interest by Cycle and AESI Type – Bar Charts	X	X
Graph 14.03.04: TEAEs of Special Interest by Cycle and AESI Type – Bar Charts	X	X
Exploratory	Dose- Escalation Part	Expansion Part
Graph 14.04.01.01.a:		
Graph 14.04.01.01.b:		
Graph 14.04.01.02.a:		
Graph 14.04.01.02.b:		
Graph 14.04.02.01.a:		
Graph 14.04.02.01.b:		
Graph 14.04.02.02.a:		
Graph 14.04.02.02.b:		
Graph 14.04.02.03.a:		
Graph 14.04.02.03.b:		
Graph 14.04.03.01: Graph 14.04.03.02:		
Graph 14.04.03.03:		
Graph 14.04.04.01.a: or		
Graph 14.04.04.01.b:		
Graph 14.04.04.02.a:		
Graph 14.04.04.02.b:		
Graph 14.04.05.03.a:		
Graph 14.04.05.03.b:		
Graph 14.04.06.01:		
Graph 14.04.06.02:		
Graph 14.04.06.03: Graph 14.04.07.a:		
Graph 14.04.07.b:		
Graph 14.04.08.a:		
Graph 14.04.08.b:		
Graph 14.04.09.a:		
Graph 14.04.09.b:		

TPL N°: eTPL SA-02-01 Of SOP SA-02.08 TPL Effective Date: 31 Mar 2016 Approved in Vault: 6/30/2021

20.3 List of Derived Data Listings

All available data has to be included in the listings.

General
Listing 16.02.01.01: Screening Failures and Not-treated Subjects
Listing 16.02.01.02: Subject Disposition
Listing 16.02.01.03: Protocol Deviations
Listing 16.02.01.03.01: Covid 19 Protocol Deviations - All important PDs related to Covid-19
Listing 16.02.01.03.02: Covid-19 Protocol Deviations - All non-important PDs related to Covid-19
Listing 16.02.01.03.03: Covid-19 Protocol Deviations - Subject listing of missed/changed visits
Listing 16.02.01.03.04: Covid-19 Protocol Deviations - Subject listing of assessments missed due to visits
impacted by Covid-19
Listing 16.02.01.04: In- and Exclusion Criteria not met
Listing 16.02.01.05: Demographic Characteristics
Listing 16.02.01.06: Baseline Disease Characteristics
Listing 16.02.01.07: Biopsy Information
Listing 16.02.01.08: Medical and Surgical History including Pre-Treatment Adverse Events
Listing 16.02.01.09: Prior Cancer Therapies
Listing 16.02.01.10: Subsequent Cancer Therapies
Listing 16.02.01.11: Procedures
Listing 16.02.01.12.01: Prior Medications
Listing 16.02.01.12.02: Concomitant Medications
Efficacy Evaluation
Listing 16.02.02.01: Target, Non-target and New Lesions Information (Including all Assessments) – Investigator
Assessments
Listing 16.02.02.02.01: Response Information (Including BOR, PFS, DoR, TOR, OS) – Investigator Assessments
Listing 16.02.02.02: Response Information (Including BOR and CBOR) – IRC Assessments
Listing 16.02.02.03: CA-125 Values and CA-125 Response (Including Time to Response)
Listing 16.02.02.04: PSA Values and PSA Response
Listing 16.02.02.05: Immunogenicity of Enapotamab Vedotin
Listing 16.02.02.06: Tumor Axl-Expression
Pharmacokinetics
Listing 16.02.02.07: Plasma/Serum Concentration of Enapotamab Vedotin (Conjugated), Enapotamab Vedotin
(Total) and Free Toxin (MMAE)
Listing 16.02.02.08: PK Parameters of Enapotamab Vedotin (Conjugated), Enapotamab Vedotin (Total) and Free
Toxin (MMAE)
,
Safety Evaluation
Listing 16.02.03.01: DLTs - Dose-Escalation Part
Listing 16.02.03.02: Exposure Data Including Dose Information, Adjustments and Interruptions
Listing 16.02.03.03: Treatment-Emergent Adverse Events
Listing 16.02.03.04: Post-Treatment Period Adverse Events
Listing 16.02.03.05: Serious Adverse Events
Listing 16.02.03.06: Fatal Adverse Events
Listing 16.02.03.07: NCI-CTCAE Grade 3 or Higher Adverse Events

	.8	Drug-induced liver injury	
4.	LIS	T OF TABLES/GRAPHS/LISTINGS	7
4.	.1	List of Statistical Tables and Graphs	7
4.	.2	List of Derived Data Listings	7
5.	VFR	SION HISTORY	

Approved in Vault: 22 Feb 2022

1. List of Abbreviations and Definition of Terms

See SAP version 4 dd. 30 June 2021.

2. Introduction

This Statistical Analysis Plan Addendum is written for the clinical trial GCT1021-01 conducted in Denmark, Belgium, UK, US, the Netherlands, and Spain (the last two added for the expansion part of the trial). The ICH guideline E3 "Structure and Content of Clinical Study Reports" is used as a guide to the writing of the plan.

In November 2020, Genmab decided to discontinue development of enapotamab vedotin but continue to offer treatment to patients who are deriving clinical benefit in the present trial. With Protocol Amendment 10, procedures and visits are reduced for the 3 remaining patients active on trial treatment. For patients still in follow-up (survival follow-up, ie the time period between end of treatment period (date of last IMP + 30 days) until death), (n=47) the survival status will be collected once before final cessation follow-up following the implementation of this Protocol Amendment 10. This SAP addendum describes the analyses of the data collected until the end of the trial. This SAP addendum does not replace the previous versions but is complementary to the SAP version 4 (amendment 3) dd. 30 June 2021.

2.1 Planned Analyses

Data collected up to and including the data cut-off date of 22 March 2021 has been reported in the CSR as per SAP version 4 dd. 30 June 2021. Data collected after the 22 March 2021 data cut-off date until the end of trial (last patient end of safety follow-up on 12 November 2021) will be reported in an addendum to the CSR based on the reporting described in this SAP addendum. This reporting in the addendum to the CSR includes data from the 3 subjects who remained on treatment after 22 March 2021 as well as data from the 47 subjects who remained in the (survival) follow-up period after 22 March 2021.

Populations will be defined as described in the SAP version 4 dd. 30 June 2021. Programs from the main analyses will be reused with the same definitions and decision rules except for the definition of what constitute an AESI in the CSR Addendum.

Following outputs will be repeated from the main analyses:

- Subject disposition
- Progression free survival
- Overall survival
- TEAE by PT
- Drug-induced liver injury
- All listings of all data after the cut-off date of 22 March 2021

The following output will be added

- Time to onset of first TEAE (AESI only),
- Time to resolution (AESI only); with percentage of events with outcome of resolution
- Time to improvement of TEAE (AESI only), percentage of events with improvement; with percentage of events with improvement
- AE summary table (same categories as in the main CSR but with the AESI categories as described below and AESI leading to permanent discontinuation of the trial treatment added)
- TEAE by PT and maximum grade
- TEAE of special interest by AESI type and PT

Page 3 of 8

TPL N°: eTPL SA-02-01 Of SOP SA-02.08 TPL Effective Date: 31 Mar 2016

- TEAE of special interest by AESI type, PT and highest NCI-CTCAE Grade
- Enapotamab Vedotin Related TEAEs of Special Interest by AESI Type and PT
- NCI-CTCAE grade >= 3 TEAEs of Special Interest by AESI Type and PT
- Serious TEAEs of Special Interest by AESI Type and PT
- TEAEs of Special Interest Leading to Permanent Discontinuation of Trial Treatment
 by AESI Type and PT

The definition of AESI in the CSR Addendum:

- PN: AEs with PTs within the peripheral neuropathy MedDRA SMQ: Peripheral neuropathy SMQ [20000034] (Broad)
- Constipation: PT
- Neutropenia: PTs neutropenia, neutrophil count decreased and febrile neutropenia.

Note: As "Immune related Adverse Events", which is generally associated with immune checkpoint inhibitors, didn't result in clinically significant findings in this study, its relevance is not applicable thus will not be included in the above AESI table.

All derived dataset programs will rerun on the whole database and contain all data. A flag marking new records and changed records will be added to each derived dataset.

3. Additional outputs

All available data from the start of the trial until the end of the trial will be included in the selected tables and graphs for all patients in the study.

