### **9.1.1 Definition of Adverse Events of Special Interest (AESI)**

Adverse events of special interest (AESI) are defined as events (serious or non-serious) which are of scientific and medical concern specific to the sponsor's product or program, for which ongoing monitoring and rapid communication by the investigator to the sponsor may be appropriate. Such events may require further investigation in order to characterize and understand them.

AESIs are defined on the basis of an ongoing review of the safety data. AESIs are discussed further in Section 9.1.9 and in the IB.

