#### **9.1.9.4 Immune-related Adverse Events**

Measures for handling immune-related AEs please refer to Section [7.3.3](#).

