### **17.1.9 Adverse Events of Special Interest**

Refer to Section [9.1.9](#).

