17.2 Adverse Events

Summary tables for AEs described below will include only AEs that are treatmentemergent, i.e. AEs that started or worsened (taking into account the dates of grade changes) during the treatment period including the safety follow-up period.

Adverse events collected during the pre-treatment will be tabulated together with the medical history (by SOC and PT) and will be included in the serious AE listing (marked with a flag). Adverse events collected during the follow-up period will be tabulated separately from the treatment-emergent AEs and will be included in the AE listings (marked with a flag).

See section 4.1.1 for definition of pre-treatment, treatment and follow-up periods.

Missing or partial AE start date will be estimated in order to include events in summary tables in case of doubt (see section 4.7 for more details).

A summary table will present the number and percentage of subjects with at least one:

- Treatment-emergent adverse event (TEAE)
- TEAE related to enapotamab vedotin
- Infusion-related TEAE
- TEAE leading to permanent discontinuation of the trial treatment
- TEAE leading to drug interruption
- TEAE leading to dose reduction
- Serious TEAE
- Serious TEAE related to enapotamab vedotin
- Grade ≥3 serious TEAE
- Grade ≥3 serious TEAE related to enapotamab vedotin
- Fatal TEAE
- Fatal TEAE related to enapotamab vedotin

TPL N°: eTPL SA-02-01 TPL Version: 02

Of SOP SA-02.08
TPL Effective Date: 31 Mar 2016
Approved in Vault: 6/30/2021

- Grade ≥3 TEAE
- Grade ≥3 TEAE related to enapotamab vedotin
- Grade ≥3 TEAE leading to permanent discontinuation of the trial treatment
- TEAE of special interest (AESI): constipation, neutropenia, peripheral neuropathy, vomiting, diarrhea, hyponatremia and possibly other types of adverse events¹
- TEAE of special interest (AESI) leading to permanent discontinuation of the trial treatment: constipation, neutropenia, peripheral neuropathy, vomiting, diarrhea, hyponatremia and possibly other types of adverse events²
- Grade 1 TEAE of special interest by type
- Grade 2 TEAE of special interest by type
- Grade 3 TEAE of special interest by type
- Grade 4 TEAE of special interest by type
- Grade 5 (fatal) TEAE of special interest by type
- Medication errors and overdose TEAEs

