The AE summary table will also be repeated for all subjects on 2.2 mg/kg across escalation and expansion, all subjects on 1.0 mg/kg across escalation and expansion, and all patients across escalation and expansion (i.e. three columns).

The following tabulations will be presented by PT (order by decreasing frequency), by SOC and PT (order by decreasing frequency of SOC and by decreasing frequency of PT within SOC) and by SOC or type, PT and highest NCI-CTCAE grade (order by decreasing frequency of SOC or type and by decreasing frequency of PT within SOC) as indicated:

- All TEAEs by PT
- Most frequent (20%) TEAEs by PT
- All TEAEs by SOC and PT
- All AEs during the follow-up period by SOC and PT and highest NCI-CTCAE grade
- All TEAEs by SOC and PT and highest NCI-CTCAE grade²
- TEAEs related to enapotamab vedotin by PT
- TEAEs related to enapotamab vedotin by SOC and PT
- TEAEs related to enapotamab vedotin by SOC and PT and highest NCI-CTCAE grade³
- NCI-CTCAE grade ≥3 TEAEs by PT
- Most frequent (5%) NCI-CTCAE grade ≥3 TEAEs by PT

Page 30 of 46

TPL N°: eTPL SA-02-01 Of SOP SA-02.08 TPL Effective Date: 31 Mar 2016

¹ AEs of special interest will be tabulated by AESI type. The AESI types will be defined using MedDRA SMQ lists or preferred term lists provided by sponsor at the time of the analysis programming.

² AEs of special interest will be tabulated by AESI type. The AESI types will be defined using MedDRA SMQ lists or preferred term lists provided by sponsor at the time of the analysis programming.

³ Only most frequent AEs (> X% of Any Grade overall) will be included. The X% will be defined at the time of the analysis programming.

Version: 4.0

- NCI-CTCAE grade ≥3 TEAEs related to enapotamab vedotin by PT
- NCI-CTCAE grade ≥3 TEAEs by SOC and PT
- TEAEs leading to permanent discontinuation of the trial treatment by PT
- TEAEs leading to drug interruption by PT
- TEAEs leading to dose reduction by PT
- TEAEs of special interest by type and PT
- TEAEs of special interest by type and PT and highest NCI-CTCAE grade
- TEAEs of special interest related to enapotamab vedotin by type and PT
- NCI-CTCAE grade ≥3 TEAEs of special interest by type and PT
- Serious TEAEs of special interest by type and PT
- TEAEs of special interest leading to permanent discontinuation of the trial treatment by type and PT

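### The SAP addendum drops immune-related AEs, a protocol AESI, from its AESI tables for a reason drawn from the results, so their grouped patient-level summary is lost

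*SAP*

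**What the plan says.** **Protocol v11.** Section 9.1.1 points the reader to one place for the list: "AESIs are discussed further in Section 9.1.9 and in the IB". It adds that "AESIs are defined on the basis of an ongoing review of the safety data". Section 9.1.9 has four subsections: constipation, neutropenia, peripheral neuropathy and "9.1.9.4 Immune-related Adverse Events". The last contains only a cross-reference, "Measures for handling immune-related AEs please refer to Section" 7.3.3, where Table 8 sets out the immune-related event groups. For the period after Amendment 10, "17.1.9 Adverse Events of Special Interest" refers back to 9.1.9 without change.

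**SAP v4 (30 June 2021).** Section 17.2 gives the AESI types as "constipation, neutropenia, peripheral neuropathy, vomiting, diarrhea, hyponatremia and possibly other types of adverse events". Immune-related AEs are not named. A footnote leaves the content open: "The AESI types will be defined using MedDRA SMQ lists or preferred term lists provided by sponsor at the time of the analysis programming". Section 4.9, on changes from the protocol, does not mention the AESI list.

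**SAP addendum (22 February 2022).** Section 2.1 reuses the main definitions with one exception, the AESI definition. It fixes three types: peripheral neuropathy (a broad MedDRA SMQ), constipation (one preferred term) and neutropenia (three preferred terms). A note then says that immune-related AEs, usually linked to checkpoint inhibitors, gave no clinically significant findings in this trial, so "its relevance is not applicable thus will not be included in the above AESI table". Section 3 states that the selected tables and graphs use all data from the start to the end of the trial, for all patients.

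**The concern.** An AESI is named so that its frequency, grade and course will be reported whatever they turn out to be. Here a category that the current protocol still lists is removed by a document written after data collection ended, and the stated reason is what the data showed. A low count of immune-related AEs would itself be the finding the category was set up to deliver. Saying that nothing clinically significant was found is a conclusion, and the addendum gives the reader no count to check it against.

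The note's appeal to relevance also sits badly with the trial's own design. The sponsor's summary of Amendment 6 attributes the section on dose modification for immune-related AEs to emerging safety data. Cohort 6 requires failure of a PD-1/PD-L1 inhibitor, and the criteria for Cohorts 2 and 8 call for prior therapy that includes one.

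At stake is a descriptive safety summary for one AESI type: how many patients had such an event, how severe it was, and when it began and resolved.

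**Working it through.** No sample-size or power figure underlies this point. The check compares the three lists, the dates, and the outputs kept and lost.

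**1. AESI lists**

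| Type | Protocol 9.1.9 | SAP v4, 17.2 | Addendum 2.1 |
|---|---|---|---|
| Constipation | listed | named | defined |
| Neutropenia | listed | named | defined |
| Peripheral neuropathy | listed | named | defined |
| Immune-related AEs | listed | not named | excluded, reason given |
| Vomiting, diarrhea, hyponatremia | not listed | named | absent, no reason given |
| Other types | – | possible | none |
| **Named types** | **4** | **6** | **3** |

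The three types in the addendum are the protocol's four minus immune-related AEs. That is the only protocol AESI removed.

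**2. Timing**

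- Data cut-off 22 March 2021 to SAP v4 on 30 June 2021: 9 + 30 + 31 + 30 = 100 days.
- Last safety follow-up 12 November 2021 to the addendum on 22 February 2022: 18 + 31 + 31 + 22 = 102 days.
- Protocol 5.1 describes the trial as open-label, and addendum 2.1 says the data to the cut-off had already been reported. The exclusion was therefore written with the results available.

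**3. What is still reported**

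- The primary AE endpoint in protocol 4.4 covers AEs, serious AEs, infusion-related AEs, Grade ≥3 AEs and related AEs. SAP v4 sections 17.2 and 17.3 tabulate these, and addendum 3.3 repeats the summary table.
- Individual terms appear by preferred term, and in SAP v4 also by organ class, highest grade, relatedness, seriousness and discontinuation.
- Some Table 8 groups have outputs of their own. Liver abnormalities are in SAP 17.5 and addendum 3.8. Laboratory shift tables include TSH, T3, T4, glucose and creatinine.

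**4. What is lost**

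The addendum's AESI tables run from A.14.03.05 to A.14.03.13, which is 13 − 5 + 1 = 9 tables. They cover incidence, highest grade, related, Grade ≥3, serious, leading to discontinuation, time to onset, time to resolution and time to improvement. None has an immune-related row. The AESI rows in summary tables A.14.03.01 and A.14.03.02 also omit them.

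**5. Whether the kept tables can replace it**

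Table 8 has nine named groups: hepatitis, pneumonitis, colitis, type 1 diabetes or hyperglycemia, hypophysitis, hyperthyroidism, hypothyroidism, nephritis or renal dysfunction, and skin toxicities. It also has a row for all others. Suppose the relevant preferred-term rows show n₁, …, n_k patients. The number with at least one such event is then known only to lie between max(nᵢ) and the smaller of Σnᵢ and the group size, because one patient may appear in several rows. Organ-class rows do not help: the groups span several classes, and each class also holds unrelated events. The AE listing in SAP 17.2 flags AESIs and infusion reactions but has no immune-related flag, so a reader would have to invent a term list and count by hand.

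**The case against.** The case on the other side is substantial. Protocol 9.1.1 lets AESIs follow ongoing safety review and also points to the Investigator's Brochure, which is not available here. Protocol section 10 plans no AESI analysis, and 10.3.6.1 leaves further AE summaries to the SAP, so the silence of SAP 4.9 carries limited weight. SAP v4 allows further AESI types and plans Table 14.03.08 to disclose the selection criteria. The addendum states that it complements SAP v4 and does not replace it, so the main report may already have grouped these events. The addendum fixes its own search terms and states the exclusion openly. Finally, 9.1.9.4 supplies no definition, the protocol describes no immune-related flag in the eCRF, and Table 8 is a management table. Any list built from it will catch events of other cause and will itself be post hoc.

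Most of this limits the size of the point. It does not remove it. Section 9.1.1 would support a documented revision of the list, but v11 still carries the category and 17.1.9 reaffirms it. The addendum cites no safety review and gives only the outcome. Disclosing an exclusion does not supply the missing count. The definitional difficulty is real and belongs in a footnote.

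Two stronger readings are tempting. A reader might infer that part of the primary safety profile was selected after the fact. The documents do not support that: the primary AE endpoint does not name AESIs, and its components are all still tabulated. SAP section 14 links the safety profile only to the safety outputs in general. A reader might also infer that immune-related AEs go unreported, or that SAP v4 excludes them. Neither holds, because the individual terms remain in the tables and listings and SAP v4 leaves its list open.

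**Conclusion.** The point holds in a limited form, as a change that should be made. A category the current protocol lists as an AESI is excluded from the addendum's AESI tables for a results-based reason, after data collection ended in an open-label trial. The loss is one of the protocol's four AESI types across nine tables and the AESI rows of two summary tables, for all patients and not only the three still on treatment after the cut-off. The summaries are descriptive, so no test or error rate is affected. The documents give no count of immune-related AEs, and the absence of clinically significant findings does not mean zero events, so no numerical size can be attached.

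This rests on two assumptions: that the Investigator's Brochure did not formally withdraw the category, and that the main report did not already present it under the open clause of SAP v4. If the main report did present it, the remaining gap is the updated, end-of-trial version.

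**What to change.** Issue a revised addendum that does the following:

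1. In 2.1, delete the exclusion note and add immune-related AE as a fourth AESI type, with a stated list of MedDRA terms mapped to the nine named event groups of protocol Table 8.
2. Change sections 3.4 to 3.6, which refer to three searches, to four. Carry the type through tables A.14.03.05 to A.14.03.13, the AESI rows of the summary tables and the AESI listing, even if counts are low or zero.
3. Label the grouping as defined post hoc, and record the AESI list as a change from protocol 9.1.9.
4. Add a footnote saying that, because no immune-related flag is described for the eCRF, the term list will also include some events of other cause and does not cover the all-other row of Table 8.

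The cost is one term list, one more AESI type in tables whose programs already exist, and a footnote. The downside is some over-counting from non-immune causes, which the footnote discloses.
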